9.3 Prohibited Concomitant Medications and Procedures

Administration of other chemotherapy, immunotherapy, antitumor hormonal therapy, other investigational therapy or other anticancer therapy during the treatment period is not allowed. Focal palliative radiotherapy or surgical intervention for non-target lesions for treatment of cancer-related symptoms is allowed during trial treatment at the discretion of the Investigator. TACE is not allowed during clinical trial treatment period. Surgical intervention

or radiation of target lesions followed for RECIST 1.1 during this trial will require discontinuation of the subject from trial treatment.

Traditional herbal or Chinese medicine for cancer (e.g., Minor Bupleurum Decoction [xiao chai hu tang] and cinobufagin [hua chan su]) is not permitted while on trial treatment and should be stopped prior to the first dose date.

Routine prophylaxis with granulocyte-colony stimulating factor (G-CSF) or granulocyte-macrophage colony stimulating factor (GM-CSF) is not allowed. These should be used with therapeutic intent and only when indicated, according to standard medical practice and Investigator judgment.

The administration of α -interferon is prohibited during trial treatment.

In vitro metabolism studies demonstrated that oxidative metabolism of ATG-008 is primarily catalyzed by CYP3A4/5, and to a limited extent CYP2C9. Hence concomitant potent CYP3A4 inhibitors (e.g., ketoconazole, clarithromycin, ritonavir) and inducers (e.g., rifampicin, phenobarbital, phenytoin, carbamezepine) are better avoided during treatment with study drug when possible. Foods and beverages containing grapefruit may be allowed. A list of common medications belonging to these classes is shown in [Appendix B](#), Sections [19.2.1](#) and [19.2.2](#).

Medications metabolized by CYP3A4/5 and CYP2C9 may be administered in this trial but subjects must be monitored for drug interactions and potentiation of toxicity. All such medication must be recorded on CRFs, including dose and dose frequency.

In vitro studies demonstrate that ATG-008 may be a moderate activator of pregnane X receptor and moderate inducer of CYP3A4/5. The in vivo magnitude of the ATG-008 induction is unknown but it might reduce the clinical effectiveness of oral or injectable contraceptives. For this reason double contraceptive methods must be used throughout the trial by fertile subjects.

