Study CC-223-CP-002 was conducted in 18 healthy adult male subjects (6 subjects in Part 1 and 12 subjects in Part 2). Subjects in Part 1 received a single 20-mg oral dose of ATG-008 capsule containing a microtracer of [¹⁴C]ATG-008 solution. Subjects in Part 2 received a single oral 20-mg dose of ATG-008 under fed or fasted conditions. ATG-008 was well absorbed systemically, as reflected by unchanged ATG-008, accounting for less than 2% of the administered dose recovered in urine and feces combined. ATG-008 represented approximately 16% of circulating TRA exposure. ATG-008 was extensively metabolized to 7 metabolites measured in urine and feces: M1, M2, M4, M7, M8, M11, and M13. Of these 7 metabolites, only M1, M2, and M13 were measurable in plasma. M1 was formed via odemethylation and was the primary circulating entity in plasma representing approximately 77% of circulating TRA exposure. Renal elimination was the primary excretion route for TRA. ATG-008 and M1 exposure were not markedly changed in healthy adult males administered a single, 20-mg oral dose of ATG-008 with or without consuming a high, fat meal. Tmax was delayed 1 and 3 hours for ATG-008 and M1, respectively, after ATG-008 was administered with a meal. These differences are expected to have minimal clinical impact.

In Study CC-223-CP-003, 14 healthy adult male subjects received ketoconazole (a strong CYP3A4 inhibitor) co-administered with a single 20 mg dose of ATG-008. After coadministration with ketoconazole (400 mg), a strong CYP3A4 inhibitor, there were moderate increases by approximately 60% and 70% increase in ATG-008 and M1 exposure, respectively, following a single 20 mg dose of ATG-008. The moderate increase was much less than the pronounced increase (>3-fold) observed in the CYP3A4 inhibition assay in vitro, suggesting a compensatory non-CYP3A4 mediated metabolism/elimination pathway, moderated the inhibited CYP3A4 activity on overall ATG-008 metabolism and elimination. These findings may be extrapolated to coadministration of ATG-008 with other moderate to strong CYP3A4 inhibitors, the resultant moderate increase in ATG-008 exposure supports clinical management rather than prospective dose adjustment of ATG-008.

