The first-in-human, phase 1/2 dose escalation and expansion clinical study (CC-223-ST-001) to assess the safety, tolerability, PK and preliminary efficacy of ATG-008 in subjects with solid tumors and hematologic malignancies, was completed in November 2016. During the dose escalation phase (phase 1), 28 subjects were treated with continuous once daily (QD) dosing across 5 dose levels: 7.5 mg (n=1), 15 mg (n=2), 30 mg (n=9), 45 mg (n=9) and 60 mg (n=7). The dose of 45 mg QD was selected for the expansion phase (phase 2) of this study which was conducted in 198 subjects across 7 tumor types including HCC, non-small cell lung cancer (NSCLC), glioblastoma multiforme (GBM), hormone receptor positive breast cancer (HRPBC), neuroendocrine tumor (NET) of non-pancreatic origin, diffuse large B-cell lymphoma (DLBCL) and multiple myeloma (MM). CC-223-ST-001 is the sole study evaluating HCC subjects to date.

Study CC-223-NSCL-001 evaluated the safety, tolerability, and PK of single- and multiple-ascending doses of CC-223 combined with either erlotinib or CC-486 (oral azacytidine) in subjects with advanced NSCLC and who had failed at least one line of standard therapy. It was a phase 1b dose escalation and expansion study evaluating escalating doses of CC-223 in combination with 2 doses of erlotinib administered concurrently with CC-223 (Arm A) or 2 doses of CC-486 administered either concurrently with CC-223 (Arm B) or sequentially with CC-223 (Arm C), followed by expansion of one or more combination cohorts at one or more selected doses. This study was terminated early, during the dose-finding phase, due to the changing landscape in NSCLC treatment and changes in the sponsor's overall strategy and portfolio management. The study was not terminated because of any specific safety concerns.

Study CC-122-DLBCL-001 (ongoing) is evaluating CC-223 as part of novel combinations with CC-122 and CC-292 administered as doublets, and as triplets in combination with rituximab, in subjects with relapsed or refractory DLBCL. As of the 2 May 2016 data cutoff date, a total of 102 subjects were enrolled into the ongoing dose escalation phase of the study.

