1.3.2.2 CC-223-ST-001 Safety

As of 1 Apr 2014, interim unaudited data are available on 226 subjects treated with ATG-008, including 28 subjects from phase 1 dose escalation, and 198 subjects from phase 2, most of whom started treatment with the MTD of 45 mg QD in continuous cycles of 28 days.

During the dose escalation phase of the study, dose-limiting toxicity (all grade 3) occurred in 4 subjects and included hyperglycemia (30 mg), rash (45 mg), fatigue (60 mg), and mucositis (60 mg). The maximum tolerated dose (MTD) was established to be 45 mg QD.

Preliminary results from this ongoing study as of the SAE database cut-off date of 1 Apr 2014, showed most frequent treatment-emergent SAEs gastrointestinal disorders (18.2%), infections (14.1%), general disorders (8.6%), metabolism and nutritional disorders (7.6%), respiratory disorders (6.6%), renal disorders (5.6%), and others < 5%. The SAEs assessed as being at least possibly related to ATG-008 included blood and lymphatic system disorders (thrombocytopenia), gastrointestinal disorders (abdominal pain, ascites, nausea, vomiting, diarrhea), general disorders (general physical health deterioration, pyrexia), infections and infestations (sepsis, infection, pneumonia), metabolic and nutrition disorders (hyperglycemia, dehydration), renal and urinary disorders (acute renal failure), and respiratory disorders (dyspnoea).

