1.3.2.3 CC-223-ST-001 Pharmacokinetics

Preliminary PK results in subjects (n = 27) in CC-223-ST-001 phase 1 indicate that ATG-008 is rapidly absorbed with peak ATG-008 plasma levels (T_{max}) achieved between 1 and 3 hours after single and multiple daily doses of ATG-008. Across the dose range of 30 mg to 60 mg, both the maximum observed concentration (C_{max}) and AUC appear to increase in a dose-proportional manner. The terminal half-life of ATG-008 is approximately 4.86 to 5.64 hours. ATG-008 plasma accumulation after multiple dosing was minimal (<25%) after repeated dosing. ATG-008 systemic exposure in humans is not markedly different from that observed in animal species administered multiple oral doses of ATG-008 at or near the maximum tolerated dose in humans (45 mg QD). The major pharmacologically-active metabolite, M1, achieved plasma exposure levels approximately 15-fold greater than parent exposure.

In dose expansion (phase 2) of CC-223-ST-001, ATG-008 and M1 plasma concentrations were measured in all subjects administered 30 or 45 mg QD ATG-008. Following single and multiple oral doses of ATG-008 at dose levels of 30 mg/day and 45 mg/day, ATG-008 was rapidly absorbed with maximum plasma concentrations occurring at a median T_{max} of 1.02 to 2.96 hours. Total body exposures (AUC_{∞}) after a single oral dose of ATG-008 appeared to increase in a dose-proportional manner from 30-mg to 45-mg dose levels. Peak exposures (C_{max}) after a single oral dose also appeared to increase in a dose-proportional manner from 30-mg to 45-mg dose levels. Maximum plasma concentrations of M1 occurred at a median T_{max} of 3.08 to 6.13 hours. Total body exposures (AUC_{τ}) of M1 after a single oral dose appeared to increase in a dose-proportional manner from 30mg to 45-mg dose levels. Peak exposures (C_{max}) of M1 after a single oral dose also appeared to increase in a dose-proportional manner from 30-mg to 45-mg dose levels. There was no apparent difference in ATG-008 or M1 PK when comparing across tumor types in phase 2.

Additionally, in HCC subjects following single and multiple oral doses of ATG-008 at dose levels of 30 mg/day and 45 mg/day, ATG-008 was rapidly absorbed with maximum plasma

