1.4 Study Rationale

There remains a high unmet medical need for effective therapies for subjects with unresectable HCC refractory to, or following failure of, at least one prior line of systemic therapy. A strong biologic rationale exists for targeting of the mTOR pathway in HCC, in particular inhibition of pAKT. ATG-008, an mTOR kinase inhibitor targeting both TORC1 and TORC2 complexes, has demonstrated promising preclinical and clinical activity against HCC, especially in HBV+ HCC subjects. Furthermore, resistance to sorafenib can be mediated by mTOR pathway activation lending further support to the development of ATG-008 in unresectable HCC in the second-line setting.

As described earlier, the greatest incidence and mortality of HBV+ HCC patients are in Asian countries (especially in China), and this contrasts sharply with western countries. It is critical to have effective treatment for patients failed at least one prior line of systemic therapy in Asian subjects.

- **Clinical efficacy: compared to the study results of Celgene, the current preliminary clinical study data of this study showed that ATG-008 treatments with 15 mg and 30 mg were effective, but the expected tumor control rate had not been observed yet. It was preliminarily considered that the best dose range of ATG-008 might have not been achieved.**

According to the results of study CC-223-ST-001-B which has been completed by Celgene, the ORR of solid tumor HCC cohort was 5.7% (3/53), among which, the best efficacy of 3 subjects (all had positive HBV) was PR and 2 of them were treated with 45 mg/QD ATG-008 (the maximum tolerated dose [MTD] of ATG-008 monotherapy was 45 mg/day, the intolerable dose was 60 mg/day).

As of 18 Jul 2019, the preliminary clinical study data showed that this study enrolled a total of 35 HCC subjects (all were Asian, among which, 15 subjects were from Chinese mainland, 13 from

Korea and 7 from Taiwan. 7 subjects received oral ATG-008 at the initial daily dose of 15mg and 28 subjects received 30mg). Among 35 subjects, 1 subject achieved PR, 14 subjects achieved SD, 19 subjects achieved PD and 1 subject still received the first cycle of treatment and no efficacy evaluation has been performed yet. The survivors accounts for approximately 65.7% (23/35). The diameter of the targeted lesions of tumors decreased after treatment from baseline in 38.2% (13/34) subjects. Currently, subjects who received the longest treatment had completed 11 cycles of treatment.

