➤ **Clinical safety: the safety profile currently observed in this study was similar to the results of foreign studies completed by Celgene and that of mTOR targeted drugs**

The most common related TEAEs in study CC-223-ST-001 completed by Celgene were decreased appetite (64.2%), diarrhea (60.4%), fatigue (60.4%), hyperglycemia (60.4%), nausea (50.9%), aspartate aminotransferase increased (43.4%) and pruritus (34%).

No suspected and unexpected serious adverse reactions (SUSAR) were reported in this study. One case of DLT was observed in 15mg dose group and no DLT in 30mg group. The most frequently reported study drug-related TEAEs were skin rash and hyperglycemia (45.7% each), decreased appetite and pruritus (31.4% each), diarrhea and stomatitis (28.6% each), weight loss (22.9%), fatigue and platelet count decreased (20.0% each), white blood cell count decreased, mouth ulceration and proteinuria (17.1% each), nausea, hepatic dysfunction and hand-foot syndrome (14.3% each), discomfort and AST elevated (11.4% each).

As ATG-008 is firstly and orally administered hepatitis B virus (HBV) positive, HCC Asian subjects who have previously received at least one prior line of systemic therapy in this study, the overall safety profile of ATG-008 is similar to that of foreign clinical studies in Europe and America, and no unexpected new safety signal is reported, it is further confirmed that ATG-008 is well tolerated and further dose escalation is allowed.

➤ **Clinical PK: the PK profile of this study was similar to the PK profile of foreign patients in Europe and America**

The foreign study (Europe and America) CC-223-ST-001-Part A demonstrated that the unchanged ATG-008 showed linear relationship within the dose range of 7.5 mg~60 mg, and the exposure level of metabolite M1 also presented linear relationship with the dose.

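### Potent CYP3A4 inhibitors are only discouraged, and starting one triggers no dose step, although the reported interaction could lift daily exposure at 45 mg/QD, and less firmly at 20 mg/BID, above that of 60 mg/day

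*Combined protocol and SAP*

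**What the plan says.** - **Restriction.** Section 9.3 carries the heading of prohibited medications, but says of potent CYP3A4 inhibitors and inducers only that they "are better avoided during treatment with study drug when possible". Its mandatory monitoring sentence concerns drugs metabolised by CYP3A4/5 and CYP2C9, not inhibitors.
- **Interaction.** Section 1.3.2 (study CC-223-CP-003) gave ketoconazole with a single 20 mg dose to 14 healthy men: "there were moderate increases by approximately 60% and 70% increase in ATG-008 and M1 exposure, respectively". It extends the result to other moderate and strong inhibitors and concludes that it "supports clinical management rather than prospective dose adjustment of ATG-008".
- **Dose ceiling.** Section 1.4 gives 45 mg/day as the maximum tolerated dose and says that the "intolerable dose was 60 mg/day".
- **Doses.** Section 1.4 adds 45 mg/QD and 20 mg/BID, about 20 subjects each.
- **Dose changes.** Section 8.2.1.2 and Table 4 reduce or hold the drug in response to toxicity, mostly at grade 3 or 4. Neither has an entry for starting an inhibitor.
- **Access to inhibitors.** Section 9.2 generally permits whatever care requires. It advises against routine anti-infective prophylaxis but leaves it to the investigator.

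**The concern.** The preference for clinical management comes from a 20 mg dose. At 30 mg/QD the same interaction leaves exposure below the 60 mg/day level. The documents show no re-check for the two higher daily doses, and Section 9.3 cites only in vitro metabolism, not the measured interaction.

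The stake is patient safety. A subject on 45 mg/QD who needs a potent inhibitor may, within the current text, stay on full dose until toxicity triggers Table 4. The two dose-limiting toxicities at 60 mg were grade 3 fatigue and mucositis; for both, Table 4 allows up to 7 days of medical management before a hold or reduction. Tolerance at 45 mg was already limited: Section 1.4.1 reports dose reductions in 18/25 (72.0%) HCC subjects starting at 45 mg, against 12/28 (42.9%) at 30 mg. Inhibitor use in those subjects is not stated.

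**Working it through.** The plan has no derived figure to reproduce: the 60% and 70% are measured results, given without a confidence interval.

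**Inputs**
- Interaction factors 1.6 (ATG-008) and 1.7 (M1): Section 1.3.2.
- Daily doses: 30 mg, 45 mg, and 2 × 20 = 40 mg.
- Reference: 60 mg/day, Section 1.4.
- Proportionality: Section 1.3.2.3 says of ATG-008, from 30 to 60 mg, that "AUC appear to increase in a dose-proportional manner". Section 1.4 says that ATG-008 "showed linear relationship within the dose range of 7.5 mg~60 mg" and that M1 is also linear with dose.
- Dose-limiting toxicities: Sections 1.3.2 and 1.3.2.2 give one among 9 subjects at 45 mg and two among 7 at 60 mg.

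**1. Exposure on a potent inhibitor.** Express daily AUC as the daily dose that would give it without an inhibitor (mg-equivalents): dose × 1.6 or × 1.7. The break-even interaction is 60/dose − 1.

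| Regimen | ATG-008 | M1 | Ratio to 60 | Break-even |
|---|---|---|---|---|
| 30 mg/QD | 48 | 51 | 0.80 / 0.85 | +100% |
| 45 mg/QD | 72 | 76.5 | 1.20 / 1.275 | +33% |
| 20 mg/BID | 64 | 68 | 1.067 / 1.133 | +50% |

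**2. If the true interaction is smaller.** At +30%, +40% and +50%, 45 mg/QD gives 58.5, 63 and 67.5; 20 mg/BID gives 52, 56 and 60.

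**3. If AUC is not quite proportional.** Let AUC vary as dose^b.
- 45 mg/QD stays above 60 mg/day while (60/45)^b < 1.6, that is b < ln 1.6 / ln 1.333 = 1.63 (M1: 1.84).
- 20 mg/BID needs 2 × (20/60)^b × 1.6 > 1, that is b < ln 3.2 / ln 3 = 1.06 (M1: ln 3.4 / ln 3 = 1.11). At b = 1.2 its ATG-008 ratio to 60 mg falls to 0.86.

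The 45 mg/QD result is therefore robust to this assumption. The BID result is not, and it also needs proportionality down to 20 mg.

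**4. Strength of the 60 mg reference.** 2/7 = 28.6% (exact 95% CI 3.7 to 71.0%), against 1/9 = 11.1% (0.3 to 48.2%) at 45 mg; two-sided Fisher p = 0.55.

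**5. Effect of a step-down.** 30 mg/QD and 15 mg/BID are both 30 mg/day, so 48 / 51 mg-equivalents on an inhibitor. That is 107% / 113% of usual 45 mg exposure (48/45, 51/45) and 120% / 127.5% of usual 20 mg/BID exposure (48/40, 51/40). Going from 45 mg/QD to 20 mg/QD instead would give 32 / 34, or 71% / 76% of usual. The step-down underdoses only if the true interaction is below 45/30 − 1 = 50% (QD) or 40/30 − 1 = 33% (BID).

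**6. Subjects affected.** The documents give no rate of use. Assuming 2 to 10%: 0.8 to 4 of about 40, or 2.6 to 13 of the 130 in Section 10.3 if one group is expanded.

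**The case against.** The strongest reply is that this was a reasoned choice. The sponsor ran a dedicated interaction study, extended it to other inhibitors and chose clinical management; Section 9.3 is consistent with that. A reader might infer that the interaction was overlooked, and the documents do not support this. The Investigator's Brochure, to which Section 1.3.2.4 refers for more detail, may also contain a check at 45 mg. What remains is that the stated reason comes from a 20 mg dose and does not extend to the added regimens on the protocol's own figures.

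The comparison itself has limits, and all of them stand. Section 1.3.2 speaks of exposure, not AUC. Carry-over from one dose in healthy men to repeated dosing in HCC is assumed. Peak concentration under inhibition is not given. A temporary rise is not continuous 60 mg dosing, and the 60 mg reference is thin.

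Use is also likely to be low. Exclusion 17 removes subjects with HIV, and exclusion 19 removes those with uncontrolled active infection requiring treatment. Interruptions of up to 2 weeks are allowed, adverse events are collected throughout, and Section 4.2 says most subjects tolerated 30 mg/QD after reduction from 45 mg. These points reduce the size of the problem. None supplies a step at the moment an inhibitor is started.

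**Conclusion.** The point holds as a gap in the dosing rules. Section 9.3 advises, the dose rules react to toxicity, and nothing takes effect when a potent inhibitor is begun. If the reported interaction is an AUC effect that carries over to daily dosing, exposure at 45 mg/QD would be 20% (ATG-008) and 27.5% (M1) above that of 60 mg/day. At 20 mg/BID it would be 6.7% and 13.3% above. The first result needs an interaction of only +33%; the second needs +50% and near-exact proportionality. The case is firm for 45 mg/QD and weaker for BID.

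A reader might go further and infer that subjects on an inhibitor would be at a proven intolerable exposure. The documents do not support that: the data shown behind the label are 2 events in 7 subjects on continuous dosing. Nor do they show that inhibitors caused the 72.0% reduction rate at 45 mg. Few subjects are likely to be affected, and the ORR test is not at issue. This is a cheap improvement.

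**What to change.** Add to Section 9.3:

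> Potent CYP3A4 inhibitors should not be given to subjects on 45 mg/QD or 20 mg/BID unless no alternative exists. If one is unavoidable, reduce ATG-008 from the first inhibitor dose (45 mg/QD to 30 mg/QD; 20 mg/BID to 15 mg/BID). The prior dose may be resumed after the inhibitor is stopped and washed out according to its prescribing information; the one-cycle wait in 8.2.1.2 does not apply. Record these reductions as inhibitor-related and summarise them separately from toxicity-related dose modifications. Delay Day 15 PK sampling, or flag it, if affected.

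Mark the potent inhibitors in Appendix B, whose list is ungraded and puts ketoconazole beside cimetidine and grapefruit juice.

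**Cost.** A short amendment. Both reduced doses are existing levels in Section 8.2.1.2, and the 15 mg and 30 mg tablets are already supplied (Section 8.1). Sample size and visits do not change, apart from any delayed PK day. Section 10.7 gains a separate summary line, so that precautionary reductions do not inflate the tolerability counts; using the rule in both randomised groups keeps those counts comparable.

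**Downside.** Exposure is lower than intended during the inhibitor course if the true interaction is below +50% (45 mg/QD) or below +33% (20 mg/BID), and investigators lose a little flexibility.

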9.4 Required Concomitant Medications and Procedures

See Section 9.1 for details. In addition, all subjects may receive BSC as clinically indicated.

10. STATISTICAL ANALYSES

10.1 Overview

This is an Asian multi-regional clinical trial (MRCT) in which ATG-008 will be administered orally to hepatitis B positive (HBV+) HCC subjects who have received at least one prior line of systemic therapy.

According to the previous study results, the sponsor will plan to continue to enroll approximately 40 hepatitis B virus (HBV) positive, unresectable HCC subjects who have received at least one prior line of systemic therapy. Among which, approximately 20 subjects will receive oral ATG-008 at an initial dose of 45 mg/QD and another 20 subjects will receive oral ATG-008 at an initial dose of 20 mg/BID. The pharmacokinetic (PK) samples will be collected from 10 subjects each in the two dose groups so as to further evaluate the PK profile of ATG-008 and its metabolites.

If ORR of tumor is greater than 15% in the study dose group (45 mg/QD or 20 mg/BID), this study will be expanded to enroll additional approximately 110 subjects using ORR as the primary study endpoint, to further evaluate the efficacy and safety of ATG-008.

It is designed as an open-label phase 2 trial evaluating the pharmacokinetics (PK), tolerability and efficacy of oral ATG-008 administered daily until the radiologic disease

progression (according to RECIST 1.1) or intolerable toxicity.

The sections below provide an overview of the proposed statistical considerations and analyses. The final statistical analysis methods will be documented in detail in the Statistical Analysis Plan (SAP).

